4.4. Study Endpoints

4.4.1 Primary Endpoints

Primary endpoints will be assessed using descriptive statistics. The statistical approaches are described Section 13.3 and will be detailed in the Statistical Analysis Plan (SAP) that will be developed and finalized before any analyses are undertaken.

- Number/Incidence of adverse events (AEs), and serious adverse events (SAEs) graded using the National Cancer Institute (NCI) Common Terminology Criteria for Adverse Events (CTCAE) version 5.0.
 - Number/Incidence of AE's related to clinically significant ECG/cardiac abnormalities

- Number/Incidence of AE's related to Heart Rate
 - Tachycardia (HR>100 bpm)
 - Bradycardia (HR < 50 bpm)
- Number/Incidence of AE's related to Blood Pressure
 - Hypotension
 - Hypertension
- Number/Incidence of AE's related to Liver Function
 - Liver function tests
- Number/Incidence of AE's related to Kidney Function
 - Renal function tests
- Number/Incidence of Mental and Psychotic AE's

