9.4. Criteria for Termination or Suspension of the Study

The study will be fully enrolled and completed as planned unless one or more of the following criteria are satisfied that require temporary suspension of the study.

- New information regarding the safety or efficacy of the study drug indicates a significant change in the known risk/benefit profile for the drug, such that the risk is no longer acceptable for subjects participating in the study.
- Significant violation of Good Clinical Practice (GCP) that compromises the ability to achieve the primary study objectives or compromises subject safety.
- Study-specific criteria for suspension of the study:
 - The study will be paused if:
 - One participant experiences any of the following during the treatment phase of the trial starting at the time of study drug administration and through Study Day 30/ EoT, even if the participant prematurely discontinued further involvement in the trial:
 - A CTCAE Grade 3 – 5 toxicity which is possibly or probably related to study treatment,
 - A suicide attempt,
 - A marked prolongation of QT interval (i.e., $QT \geq 450$ msec) over a series of 3 ECGs performed within 5-6 minutes,
 - A serious episode of psychosis as determined by the Investigator that requires immediate medical attention,
 - A severe, non-serious, AE possibly related to study treatment,
 - Two participants experience: One or more serious AE's possibly or probably related to study treatment.

The study might also be terminated by the sponsor for the following reasons:

- Slow patient enrollment,
- Data collected lacking quality,
- Poor adherence to protocol,
- Other findings that could lead to the study not meeting its objectives.

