10. ADVERSE EVENTS

An AE is defined as any untoward or unfavorable medical occurrence in a clinical research study that is observed, measured or reported by a participant, including any abnormal sign (e.g., abnormal physical exam or laboratory finding), symptom or disease, temporally associated with the participants' involvement in the research, whether or not considered related to participation in the research. This definition includes concurrent illnesses or injuries and exacerbation of pre-existing conditions.

An unexpected AE is one that is not listed in the current Investigator's Brochure or an event that is by nature more specific or more severe than a listed event.

All AEs will be monitored by the Investigator or site staff until resolution or, if the AE becomes chronic, a cause identified. If an AE is unresolved at the conclusion of the study, a clinical assessment will be made by the Investigator and/or Medical Monitor as to whether continued

follow-up of the AE is warranted.

All adverse events will be recorded in the participant's medical record and in the AE form of the eCRF.

The severity of events will be determined by the Investigator as:

- Mild: no limitation in normal daily activity
- Moderate: some limitation in normal daily activity
- Severe: unable to perform normal daily activity

The relationship of the study drug to an AE will be determined by the Investigator, based on the following definitions:

- Not Related

The AE is not related if exposure to the investigational product has not occurred, or the occurrence of the AE is not reasonably related in time, or the AE is considered unlikely to be related to use of the investigational product, ie, there are no facts (evidence) or arguments to suggest a causal relationship, or the AE is more likely related to the participant's pre-existing condition.

- Possibly Related

The administration of the investigational product and the AE are considered reasonably related in time and the AE could be explained by causes other than exposure to the investigational product.

- Probably Related

Exposure to the investigational product and AE are reasonably related in time and the investigational product is more likely than other causes to be responsible for the AE, or is the most likely cause of the AE.

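### Section 9.4's one-participant pause trigger for severe AEs excludes serious events and, read literally, probably related ones, so some severe events below CTCAE Grade 3 face a looser rule

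*Protocol*

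**What the plan says.** Protocol section 9.4 lists study-specific criteria for pausing. Three of them depend on relatedness to study drug:

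- One participant with a CTCAE Grade 3-5 "toxicity which is possibly or probably related to study treatment".
- One participant with "A severe, non-serious, AE possibly related to study treatment".
- "Two participants experience: One or more serious" AEs, possibly or probably related.

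Three further one-participant triggers carry no relatedness condition: a suicide attempt, QT prolongation confirmed over three ECGs, and a serious psychotic episode needing immediate attention.

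Severity is recorded on two scales. Section 4.4.1 has AEs and SAEs "graded using the National Cancer Institute (NCI) Common Terminology Criteria for Adverse Events (CTCAE) version 5.0". Section 10 has the Investigator rate each event mild, moderate or severe, with "Severe: unable to perform normal daily activity". No mapping between the scales is given, and section 12.3 plans separate summaries for severe events and for CTCAE grade. Section 10.2 notes that severity and seriousness do not imply one another.

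Section 10 makes possible and probable relatedness distinct classes. For a possibly related event, "the AE could be explained by causes other than exposure to the investigational product". For a probably related one, "the investigational product is more likely than other causes to be responsible for the AE".

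**The concern.** A pausing rule should respond at least as strongly to a worse or more clearly drug-related event as to a milder or less certain one. The severe-AE bullet breaks that order in two ways. It is restricted to non-serious events, so a severe event that is also serious drops to the two-participant rule. It also names only possible relatedness, where the other two relatedness-based bullets name both classes.

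The primary objective is safety, and section 9.4 is the automatic part of the safety rule. Section 4.1 allows up to 8 participants to be dosed at the same time. If a first severe, serious, related event does not trigger a pause, a further group could be dosed before a second event is seen.

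**Working it through.** The protocol states no operating characteristic for the rule, so there is no figure to reproduce. The check is an enumeration.

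**Step 1: events that could be affected.** Any related Grade 3-5 event pauses on one participant whether or not it is serious. The three named events also pause on one. What remains is an AE that is severe on the Section 10 scale, below CTCAE Grade 3, related, and not a named event. The protocol permits this combination because it uses both scales without a mapping. It does not reproduce the CTCAE definitions, so how often it occurs cannot be derived.

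**Step 2: classes.** 2 levels of seriousness × 2 levels of relatedness = 4 classes. The table shows the number of participants needed for a severity, grade or serious-AE trigger to pause the study.

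| Class (severe, below Grade 3) | As written, literal | Possibly read as a minimum | Bullet reworded (see fix) | CTCAE grade in place of the bullet |
|---|---|---|---|---|
| Non-serious, possibly related | 1 | 1 | 1 | none |
| Non-serious, probably related | none | 1 | 1 | none |
| Serious, possibly related | 2 | 2 | 1 | 2 |
| Serious, probably related | 2 | 2 | 1 | 2 |
| Classes at one / second participant / no trigger | 1 / 2 / 1 | 2 / 2 / 0 | 4 / 0 / 0 | 0 / 2 / 2 |

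Reading possibly as a minimum repairs the second row only. The two serious rows stay looser than the non-serious ones because of the word non-serious. The last column shows that relying on CTCAE grade alone would leave the group worse off than now.

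**Step 3: what one versus two participants means (illustration only).** Take N = 24 treated (section 12.2), and let p be an assumed per-participant rate of severe, serious, related AEs below Grade 3. The documents give no such rate. Count only events of this kind and treat participants as independent:

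- one-participant rule: P(pause) = 1 − (1 − p)^24
- two-participant rule: P(pause) = 1 − (1 − p)^24 − 24p(1 − p)^23

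| Assumed p | Two-participant rule | One-participant rule |
|---|---|---|
| 1% | 2.4% | 21.4% |
| 2% | 8.3% | 38.4% |
| 5% | 33.9% | 70.8% |
| 10% | 70.8% | 92.0% |

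The second participant's serious AE need not itself be severe, so other related serious AEs would raise the two-participant figures. The table gives scale across a range of assumptions. It is not a forecast.

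**The case against.** **The group may be empty.** The documents offer no example of an event that prevents normal daily activity yet grades below 3. For the serious classes the event must also meet a section 10.2 criterion and still grade below 3. Section 9.2 says no SAEs have been reported in psilocybin studies. This stands as a limit on size. It does not rescue the wording: if severe always meant Grade 3 or higher, the bullet would add nothing to the Grade 3-5 trigger. It is either redundant or inconsistent.

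**Possibly is naturally a minimum.** An investigator would hardly decline to pause because an event was more clearly drug-related. This is a fair reading and it closes the gap for probably related non-serious events. It leaves the serious classes untouched.

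**Other safeguards exist.** Section 9.4 itself allows suspension if "New information regarding the safety or efficacy of the study drug indicates a significant change in the known risk/benefit profile for the drug", making continuation unjustifiable. The Investigator may terminate at any time (7.3). SAEs reach the Investigator within 24 hours, or at latest the next working day, and are assessed with the Medical Monitor (10.4). The DSMB sees all the data (9.4.1), and its Charter is to set discontinuation criteria (11.1). All of this stands, so a first severe serious event would be reviewed promptly. But these are matters of judgement, and they do not correct the automatic rule.

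**A stronger reading to avoid.** A reader might infer that the trial would carry on regardless after a severe drug-related event, or that serious AEs in general need two participants before a pause. The documents do not support either. Related Grade 3-5 events and the named events pause on one participant, and the safeguards above apply to the rest.

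**Conclusion.** The point holds as a wording inconsistency in a safety rule, with no safety failure shown. The firm part is that, for AEs rated severe but below Grade 3 and outside the named events, a serious related event has a looser automatic trigger than a non-serious, possibly related one. The conditional part is that a probably related non-serious event meets no severity, grade or serious-AE trigger, which is true only if possibly is read literally.

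Of four classes, one pauses on a single participant under the literal reading and two do if possibly is a minimum. These are counts of logical classes and say nothing about frequency, which is unknown. The conclusion assumes that the Section 10 rating and the CTCAE grade can differ, which the protocol allows but does not show to happen. No endpoint or analysis is affected. The correction is worth making because it is small and the rule is meant to act automatically.

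**What to change.** Reword the bullet in section 9.4 along these lines: *A severe AE (serious or not) possibly or probably related to study treatment*. Mirror it in the DSMB Charter. All four classes then pause on one participant. The two-participant rule can stay for related serious AEs that are neither severe nor Grade 3 or higher.

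Do not delete the bullet in favour of CTCAE grade alone. A sentence relating the mild/moderate/severe scale to CTCAE grade would be a useful addition, but not a substitute.

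The cost is a few words in two documents and possibly more frequent pauses. How many more depends on the unknown event rate: few if such events hardly occur, but not slight at the higher assumed rates in the illustration.

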9.4.1 Data and Safety Monitoring Board (DSMB)

CONFIDENTIAL

A Data and Safety Monitoring Board (DSMB) will be constituted that will monitor the study and regularly review the clinical trial safety data. The full scope of responsibilities of the DSMB are outlined in the study protocol (see Section 11.1) and will be included in a DSMB Charter.

The DSMB will have access to the totality of the data to determine if the trial should continue as is, or if changes are warranted to protect the safety and wellbeing of the participants and/or if the trial should be terminated.

9.5. Medical Emergencies

If a participant experiences a medical emergency during the Study Day 1 visit, the Lead Therapist/Investigator (a licensed physician) will manage the participant during the emergency.

In the event a psychological crisis arises during the study, participants will be instructed to call the Participant Hotline as soon as possible. This call will be routed to the Investigator if it is confirmed that there is indeed a crisis. The Investigator (or a qualified designee) will be on call at all times to receive information from the Participant Hotline.

Upon learning about the psychological crisis, the Investigator will assess the AE by:

- Obtaining a detailed history of the event over the phone
- Collecting information on any concomitant medications
- Assessing expectedness, seriousness, severity, and relationship to the study drug
 - All AEs will be assessed regardless of whether they occurred prior to or after self-administration; however, only those events that occur after study drug administration can be attributed to the investigational product.

If the participant requires immediate care, s/he will be referred to the emergency department of the closest hospital. The emergency department and/or hospital staff, the participant's primary care provider, and/or the Investigator may prescribe medications or take steps to stabilize the participant and to help ameliorate and/or resolve the AE.

10. ADVERSE EVENTS

An AE is defined as any untoward or unfavorable medical occurrence in a clinical research study that is observed, measured or reported by a participant, including any abnormal sign (e.g., abnormal physical exam or laboratory finding), symptom or disease, temporally associated with the participants' involvement in the research, whether or not considered related to participation in the research. This definition includes concurrent illnesses or injuries and exacerbation of pre-existing conditions.

An unexpected AE is one that is not listed in the current Investigator's Brochure or an event that is by nature more specific or more severe than a listed event.

All AEs will be monitored by the Investigator or site staff until resolution or, if the AE becomes chronic, a cause identified. If an AE is unresolved at the conclusion of the study, a clinical assessment will be made by the Investigator and/or Medical Monitor as to whether continued

follow-up of the AE is warranted.

All adverse events will be recorded in the participant's medical record and in the AE form of the eCRF.

The severity of events will be determined by the Investigator as:

- Mild: no limitation in normal daily activity
- Moderate: some limitation in normal daily activity
- Severe: unable to perform normal daily activity

The relationship of the study drug to an AE will be determined by the Investigator, based on the following definitions:

- Not Related

The AE is not related if exposure to the investigational product has not occurred, or the occurrence of the AE is not reasonably related in time, or the AE is considered unlikely to be related to use of the investigational product, ie, there are no facts (evidence) or arguments to suggest a causal relationship, or the AE is more likely related to the participant's pre-existing condition.

- Possibly Related

The administration of the investigational product and the AE are considered reasonably related in time and the AE could be explained by causes other than exposure to the investigational product.

- Probably Related

Exposure to the investigational product and AE are reasonably related in time and the investigational product is more likely than other causes to be responsible for the AE, or is the most likely cause of the AE.

10.1. Spontaneously Reported Reactions

Commonly expected AEs, that have been compiled from the literature on psilocybin mushrooms reported in studies of human volunteers, are referred to as "spontaneously reported reactions" include transient anxiety, transient headache, transient nausea, and transient paranoia (Dinis-Oliviera 2017).

AEs that are included in the spontaneously reported reactions list will be separated in data analysis for review of expected versus unexpected AEs.

10.2. Serious Adverse Events

The Investigator (or qualified designee) is responsible for determining if an AE is a serious adverse event (SAE) or a non-serious event. An SAE is defined as any untoward medical occurrence that at any dose:

- Results in death
- Is life-threatening (i.e., the participant was, in the opinion of the Investigator, at immediate risk of death from the event as it occurred); it does not refer to an event which hypothetically

might have caused death if it were more severe

- Requires or prolongs inpatient hospitalization
- Results in persistent or significant disability/incapacity (i.e., the event causes a substantial disruption of a person's ability to conduct normal life functions)
- Results in a congenital anomaly/birth defect
- Requires intervention to prevent permanent impairment or damage
- Is an important and significant medical event that may not be immediately life-threatening or resulting in death or hospitalization, but based upon appropriate medical judgment, may jeopardize the patient/participant or may require intervention to prevent one of the other outcomes listed above

AEs which do not fall into these categories are defined as non-serious. It should be noted that a 'severe' AE need not be serious in nature and that a SAE need not, by definition, be severe.

In addition, any pre-existing event or condition that results in hospitalization should be recorded in the medical history and in the eCRF. The hospitalization would not result in the event or condition being reported as a study-related SAE unless, in the view of the Investigator, hospitalization was prolonged as a result of participation in the clinical trial or was necessary due to a worsening of the pre-existing condition.

Hospitalization for cosmetic procedures, non-emergency prophylaxis, or abortion does not result in an SAE report unless, in the view of the Investigator, hospitalization for these procedures was prolonged as a result of participation in the clinical trial.

10.3. Adverse Event Collection

All AE and SAEs will be collected during the entirety of the participant's involvement in the trial. If a new AE/SAE is reported >30 days after Study Day 1 and up until the 3-month, LTFU visit, it will be recorded in the participant's medical record and the eCRF; however, unless the event is deemed to be possibly or probably related to the study drug, it will not be recorded as an adverse event.:

- Events related to planned treatments or physician visits for baseline conditions collected in the medical history will not be collected unless there is an exacerbation of the condition.
- Any AE leading to withdrawal from continued participation in the trial protocol will be collected throughout the study.
- All AEs related to changes in psychiatric status will be collected throughout the study.

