7.1.2 Pre-screening

Prospective participants may be interviewed by telephone to determine whether they might be suitable candidates to participate in the trial. At the start of the telephone interview, interviewees will provide verbal consent confirming that they are willing to share personally identifiable information and their personal health information to determine if they are likely to qualify for participation in the trial.

The pre-screening interview will include questions about the participant's medical and psychiatric history, current treatment, etc. The interviewees will be asked to provide responses to the 17-question Life Events Checklist for DSM-5 (LEC-5) and the 20-question PTSD Checklist for DSM-5 (PCL-5). Qualified study site staff will provide individuals that pass the pre-screening assessment with IRB-approved study information and consent materials for review and consideration.

- If the prospective participant is not eligible or not interested in taking part in the trial their personal information will be destroyed at, apart from the summary reason for ineligibility, which will be retained on the Screening Log. An eCRF will not be completed for candidates who are not enrolled.

Pre-screening information will be retained for candidates who provide specific permission via verbal consent for utilization and retention of this information and who and provide written informed consent to participate in the trial. The Screening Log will be completed to include the qualified participant's screening number. The Screening Log will be maintained and kept up-to-date and be available for review by the study site monitor.

Table 1

Schedule of Events

Activity	Pre-Screen	Screening Period		Day 1	Day 2	Day 4 (Virtual)	Day 8 (±1 day)	EoT Day 30 1 Month (±5 days)	LTFU 3 Month (±7 days)
		-30 - to -1 (Can be extended)							
			Prior to Study Day 1						
Pre-Screen Verbal Consent ¹	X								
LEC-5 [^]		X							
PCL-5 [^]		X							
Informed Consent		X							
Medical History	X	X		X	X	X	X	X	X
Concomitant Medications	X	X		X					
Eligibility Criteria	X	X		X					
Height / Weight ²		X					X	◆ ¹⁴	
Physical Exam ³		X					X	◆ ¹⁴	
Vital Signs ⁴		X		X	X		X	X	X
Urine Pregnancy Test ⁵		X							
Urine Drug / Alcohol Tests		X		X				X	X
Clinical Laboratory Tests ⁶		X ⁶		X			X	X	
Electrocardiogram ⁷		X		X			X		
Dispense/Collect Wearable		X						◆ ¹⁴	X
Saliva – Epigenetic Test				X			X	◆ ¹⁴	
Pharmacokinetic Test ⁸				X					
Administer Study Drug				X					

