If the participant prematurely discontinues from the trial, this will be their last study visit, unless there is an ongoing adverse event that will continue to be monitored until resolution or until the Investigator and Medical Monitor determine that no additional follow-up is medically necessary.

Otherwise, the participant will return to the study site for the final 3-month, LTFU, visit.

7.1.9 3-Month Long-Term Follow-up (LTFU) Visit

Approximately three months (i.e., 90 days) after Study Day 1, participants will return for the final, 3-month, Long-Term Follow-up (LTFU) visit. At this visit, a number of protocol-mandated tests, examinations, assessments and procedures will be done as described below.

- Inquire about any changes in the participant's health in a non-suggestive manner; however, any changes noted will not be considered adverse events unless they either were noted prior to the Study Day 30 / EoT visit and/or are considered to be 'possibly' or 'probably' related to study drug administration.
- Review concomitant medications/therapies (including psychotherapy and healthcare utilization).
- Perform a brief physical exam and obtain weight (only if Study Day 8 visit was not completed).

CONFIDENTIAL

- Obtain vital sign measurements.
- Obtain urine samples for:
 - Qualitative rapid urine drug screen.
 - Qualitative urine ethyl glucuronide (EtG) test to assess alcohol consumption.
- Review participant's use of health tracking wearable device and collect the device and download the data to the trial database.
- Administer and/or have the participant complete the following clinician rating scales and participant QoL and PRO instruments, respectively:
 - GAD-7
 - PHQ-9
 - BPI
 - NIH HEALS
 - C-SSRS
 - AUDIT
 - DUDIT

Upon completion of the 3-month, long-term follow-up visit and after the study site staff obtain all outstanding data, participants will have completed the study, except if there is an ongoing adverse event that the Investigator and/or Medical Monitor believe warrants continued monitoring until resolution or until it is determined that no additional follow-up is medically necessary.

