8. SAFETY ASSESSMENTS

8.1. Adverse Events

AEs and SAEs will be noted at each study visit. Participants will be queried to determine if anything has changed in their health status since the last visit (following Study Day 1), using non-leading questions. [For AE collection and reporting requirements, see [Section 10](#) of the protocol.]

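### Sections 10.3 and 7.1.9 decide whether a late event counts as an AE by two different cut-offs, neither based on onset, so unrelated events that began within 30 days of dosing can leave the all-cause count

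*Protocol*

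**What the plan says.** Section 10.3 first states that all AEs and SAEs are collected for as long as the participant is in the trial. It then limits this: "If a new AE/SAE is reported >30 days after Study Day 1 and up until the 3-month, LTFU visit", the event goes into the medical record and the eCRF, but "unless the event is deemed to be possibly or probably related to the study drug, it will not be recorded as an adverse event". Two bullets below keep AEs concerning psychiatric status, and AEs that lead to withdrawal, under collection throughout the study.

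Section 7.1.9 (LTFU visit) words the rule differently: "any changes noted will not be considered adverse events unless they either were noted prior to the Study Day 30 / EoT visit", or are judged possibly or probably related.

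The EoT visit has a tolerance. Its column in Table 1 is headed "EoT Day 30 1 Month (±5 days". The visit before it is Day 8 ±1 day, and none is scheduled between them. Section 8.1 gives the method of elicitation: "Participants will be queried to determine if anything has changed in their health status since the last visit". For the EoT visit, the synopsis and Section 4.1 have participants assessed for AEs with no relatedness condition. They attach one only to the LTFU visit.

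The first primary endpoint in Section 4.4.1 begins "Number/Incidence of adverse events (AEs), and serious adverse events (SAEs) graded using the National Cancer Institute (NCI" and is not restricted to related events. Section 10 defines an AE "whether or not considered related to participation in the research". Section 12.3 defines a treatment-emergent AE by when it develops or worsens after treatment, with no end date.

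**The concern.** The date of report and the date of the EoT visit depend on scheduling and on when a participant happens to mention something. Neither describes the event. Two participants with the same event starting on the same day can therefore be counted differently because one attended EoT on Study Day 30 and the other on Study Day 33.

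This touches the primary endpoint. EoT is the only scheduled occasion for collecting events from about the second to the fourth week. If a compliant EoT visit falls after the 10.3 cut-off, that visit's own AE assessment comes under a filter that the visit descriptions do not impose. Relatedness is judged by the investigator in an open-label, single-arm trial, so the all-cause count is the summary that does not depend on that judgement.

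**Working it through.** No stated figure needs reproducing. The check is calendar arithmetic on the protocol's own windows, followed by applying both rules to example events.

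**Inputs.** Study Day *d* is *d* − 1 days after Study Day 1. EoT is Study Day 30 ± 5 (Table 1). The preceding visit is Study Day 8 ± 1 (Table 1). Up to 24 participants are treated (Section 12.2).

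**Step 1: where the 10.3 cut-off falls.** More than 30 days after Study Day 1 means *d* − 1 > 30, so *d* ≥ 32. The last day inside the period is Study Day 31.

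**Step 2: EoT days beyond it.** Permitted days are 25 to 35, which is 11 days. Those with *d* ≥ 32 are 32, 33, 34 and 35: 4 of 11. If the cut-off is read loosely as after Study Day 30, Day 31 joins them: 5 of 11.

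**Step 3: onset days exposed at a late EoT.** These run from the day after the preceding visit through Study Day 31.

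- Preceding visit on Day 7: 31 − 7 = 24 onset days
- on Day 8: 31 − 8 = 23
- on Day 9: 31 − 9 = 22

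**Step 4: onset days left after an early EoT.** With EoT on Day 25, Study Days 26 to 31 remain: 31 − 25 = 6 days. With EoT on Day 30 one day remains, and from Day 31 none. An event starting in this gap and first noted at LTFU fails the 7.1.9 test unless it is judged related.

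**Step 5: both rules applied.** Each event is judged not related, is not psychiatric and does not lead to withdrawal.

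| Event | Onset, days after Day 1 | Section 10.3 | Section 7.1.9 |
|---|---|---|---|
| Onset Day 12, first mentioned at EoT on Day 33 | 11 | Reported at 32 days: not an AE | Noted at EoT, not before it: unclear |
| EoT on Day 25, onset Day 27, first mentioned at LTFU on Day 90 | 26 | Reported at 89 days: not an AE | Not noted before EoT: not an AE |
| Onset Day 15, first mentioned at LTFU on Day 90 | 14 | Reported at 89 days: not an AE | Not noted before EoT: not an AE |
| Onset Day 28, telephoned in on Day 33, EoT on Day 35 | 27 | Reported at 32 days: not an AE | Noted before EoT: passes |

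All four began within 30 days of Study Day 1. In the last row the two sections give opposite answers.

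**Step 6: size per participant.** If a participant's only event is affected, incidence falls by 1/24 = 0.0417, or 4.2 percentage points.

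**Step 7: after the change.** With a boundary on onset through Study Day 31, the number of onset days exposed to reclassification by visit or report date is 0 for every permitted EoT date.

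**The case against.** The best defence is that the intent is clear: all-cause AEs through the EoT visit, and only related or unresolved ones afterwards. The EoT descriptions carry no filter, Table 1 marks AEs at EoT, and the word new in 10.3 could mean newly arising. On that reading, the event reported at a Day 33 EoT would count. This reading is reasonable, but the operative verbs are reported in 10.3 and noted in 7.1.9, and a site must apply the text. It also leaves the LTFU cases unresolved, because 7.1.9 excludes an early-onset event first mentioned there whatever new means.

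A second defence is that deriving the treatment-emergent period belongs in the SAP. That is true of tabulation, but this rule decides at the site what is recorded as an AE in the first place.

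Several stronger readings are tempting, and the protocol does not support them:

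- **That 4 of 11 days means 36% of visits.** It is a share of permitted calendar days. The target is Day 30, and nothing indicates that visits will spread evenly over the window.
- **That every unrelated event first reported at a late EoT is lost.** Section 10.3 exempts psychiatric-status AEs and AEs leading to withdrawal, so the mental and psychotic component of the endpoint is largely protected. Cardiac, heart-rate, blood-pressure, liver and kidney events have no such exemption.
- **That the events disappear.** They remain in the medical record and eCRF. Section 10.4 also requires SAEs to be reported irrespective of causality, although 10.3 names SAEs in its counting rule.
- **That an early EoT ends all-cause recording.** Under 10.3, an event volunteered by Study Day 31 is still an AE. What is missing is a scheduled occasion to ask.
- **That the product's whole safety profile is flattered.** Counts of related events are unaffected. Only the all-cause count moves, in a descriptive study.

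**Conclusion.** The point holds in limited form. Sections 10.3 and 7.1.9 use two inconsistent cut-offs, neither tied to onset. Taken literally, they remove from the AE count some not-related events that began in the first 30 days after dosing. This conflicts with the unfiltered EoT assessment, the all-cause primary endpoint, the AE definition and the onset-based treatment-emergent definition. Section 7.1.9 also leaves events noted at the EoT visit itself undefined.

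The distortion runs one way: all-cause incidence can only fall, by 4.2 percentage points for each participant whose only event is affected, with 24 treated. The number of such participants cannot be estimated from the protocol. The events are misclassified rather than unrecorded, so they could be recovered if onset dates are held.

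The conclusion rests on two assumptions. The first is that the sections are applied as written. The second is that the first 30 days are meant to be the all-cause period. That is inferred from 10.3 and from the EoT visit, since no section defines the period by onset. The correction is worth making because it is cheap and bears on the primary endpoint. It does not call the trial design into question.

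**What to change.** Use one onset-based boundary in both 10.3 and 7.1.9. Any event with onset from dosing through 30 days after Study Day 1 is recorded as an AE whatever its cause and whenever it is reported. The relatedness filter applies only to events with onset after that day. State the last day explicitly. Study Day 31 matches the present 10.3 wording; ending at Study Day 30 would shorten that period by a day. Another last day is workable if both sections use it. The existing exemptions for psychiatric-status AEs and AEs leading to withdrawal can stay as they are.

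The cost is about two sentences, plus making sure that the AE form captures an onset date. No visit or procedure is added. The all-cause AE count may rise slightly, and onset dates first given at LTFU will rest on recall.
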